Demographic characteristics of the patient caregiver (UrApp user) and the patient will be collected from the medical chart and by participant questionnaire. Variables will include: caregiver age, gender, race/ethnicity, income level, and educational level; patient age, gender, and race/ethnicity. As one inclusion criteria for trial participation is ownership of an iPhone, examination of demographic variables will provide information on the representativeness of the cohort to the general NS population and the generalizability of study findings. Baseline self-efficacy and QoL will be assessed by surveys. Caregiver self-efficacy will be assessed by a survey adapted from the Self-Efficacy for Managing Chronic Disease 6-Item Scale (Stanford Patient Education Research Center). The survey will include 3 questions with a scale of 1/not at all confident to 10/totally confident. Patient/caregiver-reported QoL will be assessed by using the 23-item Patient-Reported Outcomes Measurement Information System - Pediatric Quality of Life Inventory (PedsQL). PedsQL was developed as part of the NIH Roadmap Initiative to create universal measures for patient-reported outcomes, and contains questions in the domains of social-peer, depression, anxiety, mobility, and function. The survey has been found to have validity and feasibility in children and adolescents with NS.²² Caregivers and patients ages 5-17 will be surveyed with parent or patient forms, respectively.

2) Outcome measures will be collected at 6 and 12 months via caregiver surveys, medical chart review, and urine protein logs (UrApp data logs for the UrApp arm). We will perform 4 follow-up attempts within a 1-month timeframe to increase survey responses. Adherence to medications will be evaluated via caregiver survey with the validated 4 question Morisky, Green, and Levine (MGL) Adherence Scale.²³ We define adherence as a score of ≥ 3 on the MGL scale. Adherence with urine monitoring will be evaluated with a newly created questionnaire (Figure 4). In addition, UrApp data log (UrApp arm)

- 1) On average in the past month, how often did you check your child's urine for protein? (Once a week, 2-4 times a week, or 5-7 times a week)
- 2) In the past month, have you reduced how often you check your child's urine because he/she is in remission? (Yes or No)
- 3) In the past month, have you increased how often you check your child's urine because he/she is in relapse? (Yes or No)

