Analysis will follow the intention-to-treat principle to preserve the integrity of the randomization. Primary outcomes, adherence with urine monitoring and medications, will be analyzed via Chi-square test to compare the proportions of adherent patients in the UrApp vs SOC arms at 6 and 12 months. Results will be presented as group proportions and difference in proportions with associated 95% CIs. In an adjusted analysis using a generalized linear mixed model, we will examine the changes over time by testing the treatment arm (UrApp vs. SOC) by time (6 and 12 months) interaction. Models will include site as a random effect and adjust for any baseline characteristic differences between groups (including sex as a variable). Self-efficacy and QoL measures will be analyzed using linear mixed models. Models will include the effect of treatment (UrApp vs. SOC), time (baseline, 6 and 12 months), and the treatment by time interaction. Study center will be included as a covariate and/or a random effect. Post-hoc pairwise comparisons will be used to compare specific points in follow-up (6 and 12 months) to baseline within and across groups. Results will be presented as differences in means with associated 95% CIs. Baseline characteristics will be included in the models as covariates in an adjusted analysis. Three-way interactions will be utilized to explore the role of demographic characteristics and their association with treatment response. While not adequately powered to conduct a moderator analysis, effect sizes will be calculated by subgroup and will inform a future, full-scale study. Delayed relapse diagnosis and hospitalizations will be compared between the treatment arms using Poisson regression under the framework of generalized linear mixed models or generalized estimating equations to account for correlated data collected from the same individuals. Baseline characteristics will be included in the models as co-variates. Analysis will be guided by [name], and carried out using SAS v.9.4 (Cary, N.C.).

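### The adjusted adherence model should report arm contrasts at 6 and 12 months with covariates fixed in advance, and each visit's test should use the centre strata; the primary comparison itself is valid

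*Combined protocol and SAP*

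**What the plan says.** All analysis text is in the combined protocol and SAP, Section 2, Study Design, Aim 1, Analysis paragraph.

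- **Primary analysis.** Each of the two adherence outcomes (urine testing and drug taking) "will be analyzed via Chi-square test to compare the proportions of adherent patients in the UrApp vs SOC arms at 6 and 12 months". The estimates to be shown are also named: "Results will be presented as group proportions and difference in proportions with associated 95% CIs".
- **Adjusted model for adherence.** The purpose given for the generalized linear mixed model is this: "we will examine the changes over time by testing the treatment arm (UrApp vs. SOC) by time (6 and 12 months) interaction". No adjusted arm difference at either visit is named.
- **Its covariates.** "Models will include site as a random effect and adjust for any baseline characteristic differences between groups (including sex as a variable"). There is no list and no criterion for what counts as a difference. The demographic pool under Baseline measures is "caregiver age, gender, race/ethnicity, income level, and educational level; patient age, gender, and race/ethnicity", which is eight variables.
- **Other outcomes, same paragraph.** For self-efficacy and quality of life, "Post-hoc pairwise comparisons will be used to compare specific points in follow-up (6 and 12 months) to baseline within and across groups", and "Baseline characteristics will be included in the models as covariates in an adjusted analysis". The count models for delayed relapse and hospitalization are framed "to account for correlated data collected from the same individuals".
- **Randomization (Aim 1, Procedures).** Permuted blocks are stratified by study center. The reason given is that center practices differ in ways that may affect outcomes, with urine-monitoring adherence as the example. The chi-square does not use the strata.
- **Baseline adherence.** Both adherence surveys are scheduled at baseline in both arms (Section 3 tables; Section 4, Baseline Visit).

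**The concern.** The adjusted model should support the primary result and feed the planned full-scale trial. As written, its one named test covers change between two follow-up visits. It gives no estimate of the adjusted effect at either visit, although the same paragraph does name follow-up comparisons for two secondary outcomes. The covariate set is settled only after looking at the arms, so two competent analysts could report different adjusted effects from the same data.

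Separately, the plan stratifies by centre because centre may matter for adherence, then tests each visit as if it did not. What is at stake is the reproducibility and usefulness of supporting results, not the validity of the primary comparison.

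**Working it through.** **1. The plan's own figure.** Inputs from Aim 1, Participants and settings: 60 randomized 1:1, 20% drop-out, 55% vs 90%, two-sided pooled Z-test at 0.05.

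- Evaluable: 60 × 0.8 = 48, or 24 per arm.
- Test: Z = (p_U − p_S) / √[p̄(1 − p̄)(2/24)]. Reject if |Z| > 1.96.
- Summing the two binomial distributions over all rejecting outcomes gives 81.96%, matching the stated 82%. The normal approximation gives 79.4%.

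This power belongs to the arm difference at a single visit.

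**2. What the arm-by-time test measures.** Let θ6 and θ12 be the arm differences at the two visits. The interaction is δ = θ12 − θ6. Baseline is not a level of time in this model, so if rates are constant over time δ = 0 for any size of benefit, on the risk or the logit scale. Simulation used 24 per arm, 50,000 replicates per cell and correlated binary visits (assumed phi 0.31-0.59):

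| Constant benefit over 55% | Arm-by-time significant | 12-month chi-square significant |
|---|---|---|
| 0 | 4.5-5.1% | 6% |
| 15 points | 4.5-5.1% | 20% |
| 25 points | 4.5-5.1% | 47% |
| 35 points | 4.5-5.1% | 82% |

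A separate simulation with a Wald test gave 5-6% under the constant 35-point benefit. If SOC falls from 75% to 55% while UrApp stays at 90%, δ = 35 − 15 = 20 points, and the test has 31-42% power. Under the constant planned benefit its 95% CI half-width is 22-28 points.

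**3. The covariate rule.** Sex is adjusted for regardless. Counting it once leaves seven of the eight demographic variables. If these are independent, the chance that at least one looks imbalanced is:

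- at p<0.05: 1 − 0.95^7 = 30%
- at p<0.10: 1 − 0.90^7 = 52%

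Correlation lowers this. For all eight variables the figures are 34%/57% if independent, 25%/43% at correlation 0.5 and 19%/34% at 0.7.

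Two versions of the rule (select at p<0.05, or at p<0.10) were compared under 55% vs 90%, with a linear-probability model at 12 months. Assumed inputs were centres of 18/10/10/10, prognostic loading 0 or 0.5 and covariate correlation 0 or 0.5, with 3,000 trials per cell:

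- adjusted differences disagree in 27-31% of trials
- mean gap where they disagree: 2.3-3.6 points
- significance disagrees in 1.6-2.9% of all trials

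In a companion run of the same design (6,000 trials per cell), type I error of each version stayed at 4.5-5.2%. Power was 80-82% with centre and sex only, 78-81% under the p<0.05 rule, 77-81% under the p<0.10 rule and 72-78% with all eight variables.

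**4. Centre strata.** In centre k, let a_k and c_k be the adherent counts on UrApp and SOC, n_Uk and n_Sk the arm sizes, N_k their sum, and m_k = a_k + c_k. Then:

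- E_k = n_Uk·m_k/N_k
- V_k = n_Uk·n_Sk·m_k(N_k − m_k)/[N_k²(N_k − 1)]
- Cochran-Mantel-Haenszel (CMH) χ² = [Σ(a_k − E_k)]²/ΣV_k
- Mantel-Haenszel risk difference = Σ[(a_k·n_Sk − c_k·n_Uk)/N_k] / Σ[n_Uk·n_Sk/N_k]

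The simulation used 200,000 replicates per cell. The documents give no centre rates, so the spreads are assumed:

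| Control rates across centres | Power: chi-square vs CMH | Type I error: chi-square vs CMH |
|---|---|---|
| no difference | 82.1% vs 81.1% | – |
| 47-66% | 82.0% vs 81.7% | – |
| 39-76% | 82.7% vs 83.7% | 4.4-4.7% vs 5.0-5.1% |
| 26-91% | 84.3% vs 88.2% | 2.6-3.0% vs 4.8-5.0% |

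**The case against.** The strongest reply is that the interaction test does what it is there for. The plan says it examines change over time, and persistence is a declared interest (the maintenance domain under Goals/Aims; use retention in Aim 2a). The effect size is already given by the unadjusted differences with 95% CIs at both visits. Rejecting about 5% of the time under a constant benefit is how any interaction test behaves. This is a 60-participant pilot, type I error is not inflated, and site is already in the adjusted model. The self-efficacy and quality-of-life models have no covariate list either, and including everything costs power.

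All of that stands, and it keeps the point modest. It does not answer two things: the plan chose to fit an adjusted model for its primary outcomes without committing to an adjusted effect, and its covariates depend on chance imbalance.

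Three stronger readings are tempting and are not supported:

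- A reader might infer that the primary result rests on the interaction. It does not; the chi-square comparisons carry it.
- A reader might infer that the adherence model ignores repeated measures. The participant term is unstated, not excluded.
- A reader might count adjustment for centre and sex alone as a third version of the rule, which raises disagreement to 40-53% of trials. That option disregards the rule, so the figure overstates the problem.

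**Conclusion.** The point holds as two modest improvements. The unadjusted comparisons at 6 and 12 months are valid and powered as stated.

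1. The adjusted adherence model should yield an arm effect at each visit from covariates fixed in advance. The harm is to reproducibility: disagreement in roughly 27-31% of trials, about 2-4 points on average where it occurs, with little effect on type I error. This rests on assumed thresholds, covariate strength and correlation, and centre sizes.
2. Analysing by the randomization strata matches the design. It costs about 1 point of power if centres do not differ, gains about 1 point at control rates of 39-76%, and gains about 4 points at 26-91%, where the unstratified test is conservative (type I error about 3%). These spreads are assumptions, so this part is minor.

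**What to change.** **Adjusted model.**

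- Replace the imbalance rule with centre, sex (state whether the child's or the caregiver's, since both are collected) and the baseline value of the same adherence measure. Fix this before anyone sees outcomes by arm, and so before the first Aim 3 stakeholder meeting, where efficacy results to date are shared.
- Report the adjusted arm contrast with 95% CI at 6 and at 12 months from one named model. A suitable choice is an identity-link GEE clustered on participant, with Mancl-DeRouen standard errors and a t reference. It reports on the risk-difference scale of the primary analysis. It also avoids the logistic model's difficulty when every UrApp family is adherent at a visit (0.9^24 = 8% of trials at 90%).
- Keep arm-by-time as supportive and the whole model secondary.

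**Caution on baseline adherence.** Section 4 opens the envelope before the baseline surveys, and the virtual option allows weekly reminders afterwards. Use the baseline value only if it was recorded before app use could affect it; otherwise keep centre and sex.

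**Primary test.** At each visit, use a centre-stratified CMH test with a Mantel-Haenszel risk difference and 95% CI, in place of or beside the chi-square. State which one is primary.

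**Cost.** SAP wording only, with no new data. With centre and sex, the GEE contrast at 12 months has 77-81% power and 3.4-4.2% type I error. A different bias-reduced standard error gave about 78% and 5-7%, so the choice must be named. The effect of adding baseline adherence was not calculated.

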Summary of work to date: We have 1) demonstrated the significance of self-management and the unmet need for a support tool in childhood NS; 2) established feasibility and interest in using mHealth interventions among NS patient caregivers; 3) soundly designed UrApp features that are grounded in theory with excellent preliminary user feedback and usability; and 4) established technical innovation and validity. *Our central hypothesis is that the use of a UrApp-based self-management support system will improve adherence with urine monitoring and medications.* We also predict that caregiver self-efficacy, patient and caregiver quality of life (QoL), and relapse detection will improve while hospitalization rates will decline.

In this proposal, we aim to rigorously test our hypotheses to gain sufficient preliminary data to advance the scalability and capacity of the intervention to impact outcomes in the real world. We plan to address crucial domains within the RE-AIM framework: efficacy (pilot trial to evaluate UrApp's impact on outcomes and stakeholder engagement to determine outcomes important to users), adoption (process evaluation to determine barriers/facilitators of app use and stakeholder involvement to refine the intervention design and create strategies to increase recruitment for a future trial), implementation (process evaluation of UrApp implementation and stakeholder involvement to redesign the intervention to ensure appropriate implementation), and maintenance (process evaluation to determine influences on use retention and user/stakeholder involvement to refine intervention design and plan a feasible clinical trial).²⁰ The “reach” domain is outside the scope of the pilot trial, though we have planned technical updates of UrApp to increase the number of iPhone versions it supports. Our specific aims are:

Aim 1. Evaluate the preliminary efficacy of UrApp among caregivers of children with nephrotic syndrome in a pilot trial. Participants will be randomized 1:1 to UrApp or SOC and followed for 1 year. Primary outcomes are medication and urine monitoring adherence. Secondary outcomes are self-efficacy, patient-reported quality of life, relapse detection, and hospitalizations.

Aim 2. In parallel with the pilot trial, perform a mixed-methods process evaluation of the

implementation of UrApp to determine the influences on its effectiveness.

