Site PIs at CHOA, OHSU, and UMn met and agreed on all procedural details, including standards for usual care, led by [name]. A Manual of Procedures was created. Each site will obtain local IRB approval (central IRB not required for a K23). Data entry and collection will be centralized via a REDCap database built by [name].

The ECPI coordinator and [name] will provide data collection and entry training to the site PIs and coordinators.

Aim 1. Evaluate the preliminary efficacy of UrApp among caregivers of children with nephrotic syndrome in a pilot trial.

Participants and settings: 60 participants will be recruited from the nephrology clinics of CHOA,

OHSU, UMn, and MUSC. Sample size of 60 participants (randomized 1:1) will achieve 82% power to detect a 35% point difference in adherence with urine monitoring (primary outcome), with 20% drop-out. Sample size and power estimates are based on an adherence rate of 55% in the control group and 90% in the UrApp intervention group. These estimates are based on our single center experience with SOC⁸ and our experience with text messaging for NS monitoring, where 94% of the participants continued to check urine and provide results via text messaging at the end of 1 year (manuscript under review). Power was calculated using a two-sided Z-test with pooled variance at 0.05 type I error rate using PASS v. 14.0.8 (Kaysville, UT). Our sample size exceeds the recommended minimum of 12 participants per arm for pilot studies.²⁰

Inclusion criteria: Caregivers of patients ages 1-17 with steroid sensitive NS diagnosed within 42 days at time of enrollment; access to WIFI/internet; and proficiency with the English language.

Exclusion criteria: end-stage kidney disease; renal transplantation; and clinical or histologic evidence of secondary NS (e.g., systemic lupus erythematosus).

Procedures: Participants will be enrolled and randomized 1:1 to UrApp or SOC treatment arms at the baseline visit between 2-6 weeks after diagnosis. Recruitment will continue for 2 years, and participant follow-up will be 1 year. Written caregiver consent and patient assent (verbal for children ages 6-10 and written for children ages 11 and above) will be obtained per local IRB guidance.

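### Self-efficacy and QoL: the mixed model does not use the collected baseline score for adjustment, which costs some precision, and its within-arm comparisons with baseline should be descriptive only

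*Combined protocol and SAP*

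**What the plan says.** The Combined protocol and SAP names these outcomes as secondary under Goals/Aims: "Secondary outcomes are self-efficacy, patient-reported quality of life, relapse detection, and hospitalizations". Section 2, Study Design, Aim 1, Analysis then sets out the method:

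- The type of model is a linear mixed model for both outcomes, and no separate change score is defined.
- On the terms in that model, the plan says: "Models will include the effect of treatment (UrApp vs. SOC), time (baseline, 6 and 12 months), and the treatment by time interaction". Baseline is therefore a level of the response, and nothing requires the arms to share a baseline mean.
- On the comparisons to be reported, it says: "Post-hoc pairwise comparisons will be used to compare specific points in follow-up (6 and 12 months) to baseline within and across groups".
- On covariates, it says: "Baseline characteristics will be included in the models as covariates in an adjusted analysis". The baseline value of the outcome itself is not named among these covariates.

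The baseline score exists. Under Measures/Materials, "Baseline self-efficacy and QoL will be assessed by surveys", and the Section 3 schedules tick both surveys at baseline, V2 and V3 in each arm.

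**The concern.** There are two issues.

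The first is precision. A model with baseline as a freely estimated response time gives a between-arm contrast that carries the sampling error of the baseline difference between arms. Randomisation says the true baseline difference is zero, and the plan does not use that fact. In a pilot expecting about 24 completers per arm, wide intervals on secondary outcomes are the main limit on what can be learned.

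The second is the comparison of each arm with its own baseline. Baseline falls two to six weeks after diagnosis, and both arms receive education and test strips. Caregiver confidence and QoL may change over the following year whatever the allocation. The plan does not say that these comparisons are descriptive, and trial results go to the stakeholder committee that will refine UrApp and plan the next trial (Aim 3).

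**Working it through.** **The plan's own figure.** Participants and settings, Aim 1: "Sample size of 60 participants (randomized 1:1) will achieve 82% power to detect a 35% point difference in adherence with urine monitoring". With the stated 20% drop-out, 60 × 0.8 = 48 completers, or 24 per arm. For 55% against 90%, two-sided 0.05, pooled Z-test, exact binomial enumeration at 24 per arm gives 81.96%, which reproduces the 82%. (The plain normal approximation gives 79.4%.) So 24 per arm is the right base. No power figure is given for self-efficacy or QoL.

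**Variance of the between-arm contrast at one follow-up visit.** Take n per arm, complete data, equal SDs at baseline and follow-up, and correlation ρ between them. In units of 2·SD²/n:

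- arm-by-time contrast (difference in change): 2(1−ρ)
- raw arm difference at follow-up: 1
- baseline score as covariate: 1−ρ²

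The covariate version relative to the change contrast is (1−ρ²)/[2(1−ρ)] = (1+ρ)/2. Relative to the raw difference it is 1−ρ².

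ρ is an assumption. With 24 per arm, half-width = 1.96·√(variance × 2/24), and the minimum detectable difference (MDD) at 80% power = (1.96+0.84)·√(variance × 2/24), both in SD units. Arrows run from the change contrast to the covariate version:

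| ρ | 2(1−ρ) | 1−ρ² | (1+ρ)/2 | SE smaller by | 95% half-width | MDD |
|---|---|---|---|---|---|---|
| 0.3 | 1.40 | 0.91 | 0.65 | 19% | 0.67 → 0.54 | 0.96 → 0.77 |
| 0.5 | 1.00 | 0.75 | 0.75 | 13% | 0.57 → 0.49 | 0.81 → 0.70 |
| 0.7 | 0.60 | 0.51 | 0.85 | 8% | 0.44 → 0.40 | 0.63 → 0.58 |
| 0.8 | 0.40 | 0.36 | 0.90 | 5% | 0.36 → 0.34 | 0.51 → 0.49 |

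At ρ = 0.5 the change contrast would need 48/0.75 = 64 completers to match 48 with adjustment.

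**With dropout.** Generalised least squares on the three-visit model used 30 per arm, the same ρ between every pair of visits, and 20% lost after baseline. A model with a common baseline mean then has 0.70, 0.79, 0.88 and 0.92 of the planned contrast's variance at ρ = 0.3, 0.5, 0.7 and 0.8.

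**Unequal SDs.** With baseline SD s₀ and follow-up SD s₁, the change variance minus the adjusted variance is (s₀² + s₁² − 2ρs₀s₁) − s₁²(1−ρ²) = (s₀ − ρs₁)². This is never negative. It is zero when the slope of follow-up on baseline, ρs₁/s₀, equals 1. For example, with ρ = 0.7 and s₁ = s₀/0.7, both are 1.04 (1 + 2.04 − 2.00, and 2.04 × 0.51).

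**Within-arm tests.** A simulation assumed no treatment effect, 24 per arm, a common improvement of 0.3 to 0.5 SD in both arms, and ρ from 0.3 to 0.7. The UrApp before-after test was significant in 22% to 85% of trials. Exactly one arm was significant in 25% to 50%; by symmetry that arm is UrApp in half of these, about 12% to 25% of trials.

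**The case against.** The planned model is standard. It defines no change score, and the arm-by-time contrast is an unbiased randomised comparison. That stands: the choice is between two valid estimators, for secondary outcomes of a pilot. A reader might infer that the planned analysis is biased or invalid; the documents do not support that.

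The size of the loss is uncertain. That also stands. A reader might infer that a quarter of the precision is given away, but that figure needs ρ = 0.5, equal SDs and complete data, and with 20% dropout the ratio there is 0.79. Nor is adjustment strictly better at every correlation below 1. The gain vanishes when the slope is 1, and estimating a slope from 48 completers costs roughly 2% of variance, so with equal SDs break-even is near ρ = 2/1.02 − 1 = 0.96.

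The across-group wording could mean the arm difference at each visit. Precision is then still lost, but the pattern reverses, and the gain from adjustment is largest when ρ is high.

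The baseline characteristics in the adjusted analysis might be read to include the baseline score. The plan does not say so, and a score that is already a response level cannot sensibly also be a covariate in the same model.

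Adjustment has a practical snag. Eligibility starts at age 1, while the PedsQL parent forms listed in Section 4 start at age 2 and the child forms at age 5. A child who reaches 2 or 5 during follow-up can have a follow-up score with no possible baseline. The planned model uses such scores; a simple covariate model drops them. For the same reason, 24 per arm overstates the number with child-reported QoL.

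Finally, a reader might infer that a UrApp-only improvement will be claimed as efficacy. The plan does not say that. It labels these comparisons post-hoc and sets them beside the between-arm ones.

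**Conclusion.** The point holds as a question of efficiency and interpretation. Under either reading of the between-arm contrast, using the baseline score gives equal or smaller variance in large samples. Against the arm-by-time contrast the ratio is 0.65 to 0.90 for ρ of 0.3 to 0.8 (about 0.70 to 0.92 with 20% dropout after baseline). Against the raw follow-up difference it is 0.91 to 0.36 with complete data. These figures rest on an assumed ρ and equal SDs. The within-arm comparisons cannot show an effect of UrApp and need a descriptive label.

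One condition applies. Section 4, Baseline Visit, opens the envelope once consent is obtained and lists the surveys after education and, in the UrApp arm, after the app is downloaded. If allocation has already shifted a baseline score, the change contrast subtracts the whole shift from the effect. Covariate adjustment subtracts only the regression slope times the shift, which is less whenever the slope is below 1. So the survey order is no reason to keep the change contrast.

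The primary adherence analyses are unaffected. This should be changed, but it does not threaten the trial's validity.

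**What to change.** Replace the comparison wording for self-efficacy and QoL with the arm difference and 95% CI at 6 and at 12 months, from a mixed model that uses the baseline score in one of two ways:

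- **As a covariate:** model the 6- and 12-month scores with arm, visit, arm-by-visit, site, baseline score and baseline-by-visit.
- **As a three-visit likelihood model** with a common baseline mean in the two arms. This keeps children who had no age-appropriate PedsQL form at baseline.

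State that within-arm changes from baseline are descriptive only and carry no claim about UrApp.

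Have the baseline self-efficacy and QoL surveys completed before the envelope is opened. The document is dated 17 February 2022 and recruitment is stated to run to March 2022, so on those dates most baseline surveys will already have been taken. Where a score was taken after allocation, prefer the covariate form, which does not assert equal baseline means, and give a rule for missing baseline scores.

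The cost is a few sentences of analysis text and a change in the order of baseline steps for any remaining enrolment. No new data or visits are needed. The small downside is handling children without a baseline PedsQL form; the caregiver self-efficacy survey has no such age gap.

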Aim 2. In parallel with the pilot trial, perform a mixed-methods process evaluation of the implementation of UrApp to determine the influences on its effectiveness. Process evaluation examines the extent to which an intervention is implemented as intended and the influences on its effectiveness, and is increasingly recognized as integral to both the development and assessment of health promotional programs.²⁴ Our UrApp-based intervention program is novel in the childhood NS field; hence, we will perform process evaluation alongside the pilot RCT to increase the *rigor* of this formative process to design an effective self-management support tool. Aim 2 design is collaboratively developed by [name] and experts in behavioral and implementation sciences, Drs. [name] and [name].

Aim 2a. Evaluate UrApp engagement, use retention, and features used via user analytics and

examine their relationships with UrApp efficacy with respect to primary and secondary outcomes. One of the main purposes of process evaluation is to determine the extent to which an intervention was delivered as intended. Key elements include: *fidelity* (delivery as planned) and *dose* (quantity of the intervention delivered and extent to which participants actively engaged with the materials including initial and continued use).^{24,25} We operationalize these concepts as: UrApp engagement (frequency of use [*dose*]), retention (use over time [*dose*]), and app functions used and frequency of use (depth of use [*fidelity and dose*]).

Procedures and analysis: User behavior data are automatically captured by UrApp analytics and include information on: frequency of use, frequency of use over time, and specific app functions used and frequency. These measures will be downloaded at 6 and 12 months among participants in the UrApp arm (n=30). *A priori*, we define adequate engagement as accessing UrApp at least two times per week during the first 3 months, poor retention as a 50% decrease in weekly use over time, and adequate depth of use as transmission of data to providers for all episodes of disease relapse/remission when prompted. The relationship between user behavior and primary and secondary outcomes (detailed under Aim 1) will be assessed via Chi-square test/Fisher's exact test or t-tests or Wilcoxon rank-sum tests, as appropriate.

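### Aim 2a can relate logged app use to self-efficacy and QoL only through two-group tests; add a continuous-use estimate with a 95% CI beside the engagement and retention categories

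*Combined protocol and SAP*

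**What the plan says.** All references are to the combined protocol and SAP, Section 2, Study Design.

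- **Data (Aim 2a, Procedures and analysis).** "User behavior data are automatically captured by UrApp analytics and include information on: frequency of use, frequency of use over time". The opening paragraph of Aim 2a labels engagement and retention as dose. The data are downloaded at 6 and 12 months for the UrApp arm, n=30.
- **Cuts (same place).** "we define adequate engagement as accessing UrApp at least two times per week during the first 3 months", and "poor retention as a 50% decrease in weekly use over time".
- **Tests (same place).** The relation between user behaviour and the primary and secondary outcomes "will be assessed via Chi-square test/Fisher's exact test or t-tests or Wilcoxon rank-sum tests, as appropriate". No correlation, regression or interval estimate is listed.
- **Outcomes (Goals/Aims, Aim 1, and the Aim 1 analysis paragraph).** Self-efficacy and QoL are secondary outcomes. "Self-efficacy and QoL measures will be analyzed using linear mixed models", that is, as continuous scores.
- **Power (Aim 1, Participants and settings).** "Sample size of 60 participants (randomized 1:1) will achieve 82% power to detect a 35% point difference in adherence with urine monitoring". Aim 2a has no power figure, assumed effect or expected share above either cut.

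**The concern.** The question in Aim 2a is whether more use goes with better outcomes. Use is recorded as a number and the two outcomes are scores, yet each listed test needs at least one of them in groups. The only groups the plan defines are on the use side. A family that opens the app twice a week is then treated the same as one that opens it daily, and differently from one just below two.

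In an arm this small the split may also be lopsided. Families are told to test urine daily, and the sample-size paragraph assumes 90% adherence in the UrApp arm, where adherence is likewise set at twice a week. If most families clear the engagement cut, the comparison rests on a handful who do not.

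What is at stake is the usefulness of the dose information passed to the stakeholder committee and to the planning of the full-scale trial. The primary result is not affected.

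**Working it through.** **1. The plan's own power figure.** Inputs: 55% vs 90%, 24 per arm after 20% drop-out, two-sided 0.05, pooled Z-test.

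- Pooled proportion = (0.55 + 0.90)/2 = 0.725. Null SE = √(2 × 0.725 × 0.275/24) = 0.1289.
- Alternative SE = √((0.55 × 0.45 + 0.90 × 0.10)/24) = 0.1186.
- Normal approximation: Φ((0.35 − 1.96 × 0.1289)/0.1186) = Φ(0.82) = 79.4%.
- Exact binomial enumeration of the same test: 81.96%, which matches the stated 82%.

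The figure reproduces, but it concerns the primary comparison and says nothing about Aim 2a.

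**2. Which tests can use uncut frequency.**

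- Yes/no outcome (adherence): a t-test or Wilcoxon test can compare raw frequency between adherent and non-adherent families. Nothing need be lost.
- Continuous outcome (self-efficacy, QoL): a t-test or Wilcoxon test needs use in two groups. Chi-square or Fisher needs the outcome cut as well.

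**3. Size of the loss if the relation is linear.** Cutting a normal variable so that a share p lies above the cut c multiplies its correlation with the outcome by φ(c)/√(p(1−p)). This is 0.80, 0.76, 0.70 and 0.58 for p = 50, 70, 80 and 90%. A correlation of 0.5 becomes about 0.40, 0.38, 0.35 and 0.29.

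Power was simulated with 40,000 replicates per cell (bivariate normal log use and outcome, two-sided 0.05). A Pearson test on uncut use was compared with a t-test after the cut. The correlation and engaged share are assumptions, because the documents give neither.

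Points of power lost at 50/70/80/90% engaged:

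| Correlation | n = 24 | n = 30 |
|---|---|---|
| 0.2 | 4.1 / 4.5 / 6.0 / 8.9 | 5.3 / 6.3 / 7.2 / 10.8 |
| 0.3 | 9.9 / 11.3 / 14.1 / 19.6 | 11.8 / 14.4 / 17.1 / 23.1 |
| 0.4 | 17.1 / 20.6 / 24.7 / 34.1 | 18.8 / 23.2 / 28.2 / 39.8 |
| 0.5 | 21.4 / 26.5 / 33.8 / 48.7 | 20.9 / 26.6 / 34.2 / 50.8 |
| 0.6 | 19.4 / 25.8 / 35.4 / 56.0 | 14.5 / 20.0 / 29.2 / 51.0 |

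In absolute terms, at correlation 0.5:

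- n = 24: Pearson 73%, Spearman 66%; cut t-test 52, 47, 39 and 24%.
- n = 30: Pearson 83%, Spearman 77%; cut t-test 62, 57, 49 and 32%.

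The loss from Spearman to Wilcoxon is mostly 0 to 5 points smaller than the loss shown in the table.

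**4. Is a 90% share plausible?** If the 90% planning rate for adherence carried over to app access (an assumption), 0.10 × 24 = 2.4 families would fall below the cut, or 3 of 30. With 24 families, the chance that fewer than two do is 0.9²⁴ + 24 × 0.1 × 0.9²³ = 0.080 + 0.213 = 29%. In that case there is no usable second group.

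**5. Size of the gain from the cut if there is a true threshold.** Here the outcome is assumed to shift only above the cut, by 1.0 to 1.5 SD.

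| n = 24, shift 1.2 SD | 50% engaged | 70% | 80% |
|---|---|---|---|
| Cut t-test | 79% | 70% | 57% |
| Pearson | 55% | 44% | 31% |
| Spearman | 60% | 45% | 27% |

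Across shifts of 1.0 to 1.5 SD, 50 to 90% engaged and n = 24 or 30, Pearson has about 11 to 33 points less power than the cut.

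**The case against.** **The threshold is deliberate.** It is fixed a priori, and the same twice-a-week frequency defines adherence to urine monitoring. If benefit really starts there, the grouped test is the better one by about 11 to 33 points, and the linear simulations favour correlation by construction. This stands. A reader might infer that the categories should be replaced or kept only for description. The documents do not support that, because they do not say which shape holds.

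**The size is conditional.** A reader might infer a fixed loss of 20 to 30 points. No correlation or engaged share in the documents supports a single figure, and the loss is well below that at weak correlations. A reader might also infer that the two-group test will usually miss even a strong relation. At correlation 0.5 with 30 families it detects the relation 62% of the time if half are engaged and 57% if 70% are. The inference is true only for uneven splits or weaker correlations.

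**The aim is exploratory.** Aim 2a has no power target or decision rule, it is accompanied by surveys and interviews, and the raw counts are kept. Nothing in the plan says that a non-significant test would be reported as engagement not mattering. This also stands and limits the severity. It does not remove the point, since an exploratory aim needs an estimate with an interval and Aim 2a plans none.

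**The wording allows choice.** "exact test or t-tests or Wilcoxon rank-sum tests, as appropriate" could be read as leaving room for other methods. It chooses among the tests named, and no other section adds a correlation or regression for Aim 2a.

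**Conclusion.** The point holds in a limited form. For self-efficacy and QoL, the listed tests discard the recorded dose information in an arm of 24 to 30 families. The primary adherence outcomes need not be affected.

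If the relation is roughly linear, the cost in power is:

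- about 17 to 34 points at correlations of 0.4 to 0.5 with 50 to 80% engaged;
- about 4 to 17 points at correlations of 0.2 to 0.3 with the same shares;
- about 34 to 56 points at correlations of 0.4 to 0.6 if about 90% are engaged.

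These figures rest on an assumed correlation, an assumed engaged share, a normal model and a two-sided 0.05 level. If benefit exists only above the threshold, the advantage reverses. Even uncut, power is only about 51% at correlation 0.4 with 24 families, so the interval estimate matters more than the test. This is a cheap improvement and not an error that threatens the trial.

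**What to change.** In Aim 2a, Procedures and analysis, add an analysis that relates logged use to self-efficacy and QoL at 6 and 12 months.

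- Use mean openings per week (log-transformed or ranked) for engagement, and within-family change in weekly use for retention.
- Use Spearman correlation or linear regression, and report the estimate with a 95% CI.
- Keep the prespecified engagement and retention comparisons beside it, and report how many families fall on each side of each cut.

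Cost: a few sentences in the analysis text and one more exploratory analysis to report. The analytics are already downloaded at 6 and 12 months, so no visit, survey or data item is added. Keeping the categories protects against the case where the threshold is real.
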